### **4.2. Study Endpoints**

#### **4.2.1. Primary Efficacy Endpoint**

The primary efficacy endpoint of the study is OS, defined as time from randomization to death from any cause.

#### **4.2.2. Key Secondary Efficacy Endpoint**

The key secondary efficacy endpoint is Relapse-free survival (RFS) which is defined as time from randomization to the date of documented relapse or death from any cause, whichever occurs first.

#### **4.2.3. Additional Secondary Efficacy Endpoint(s)**

The additional secondary efficacy endpoints are:

- Time to relapse;
- Time to discontinuation from treatment;
- Patient-reported outcomes utilizing the FACIT-Fatigue Scale and the EQ-5D; and
- Measures of healthcare resource utilization.

#### **4.2.4. Safety Endpoints**

The safety endpoints include:

- Type, frequency, severity, and relationship of adverse events to study treatments;
- Physical examinations;

- Vital signs;
- Clinical laboratory evaluations;
- Concomitant medication/therapy.

[REDACTED]

[REDACTED]

[REDACTED]

[REDACTED]

[REDACTED]

[REDACTED]

[REDACTED]

The analysis methods and timing of analysis for the quality of life endpoints are described in a separate pharmacoeconomics SAP.

[REDACTED]

### **4.3. Stratification, Randomization, and Blinding**

Randomization will be carried out using an Interactive Voice Response System (IVRS). Treatment assignment will follow a 1:1 ratio between two treatment arms. Randomization method was based on permuted-block randomization. Randomization was stratified by the following factors: age at time of induction therapy (55-64 versus  $\geq 65$  years); prior history of MDS (yes versus no); cytogenetic risk category at time of induction therapy (intermediate risk versus poor risk); received consolidation therapy following induction therapy (yes versus no).

This is a double-blind study. Subjects, investigators, site staff and Celgene Corporation clinical and medical personnel will be blinded of treatment assignments until database lock.

### **4.4. Sample Size Determination**

The equality of OS curves will be compared between the oral azacitidine and placebo treatment arms using a stratified log-rank test. Assuming a median OS of 16 months in the placebo treated group ([REDACTED]), a median OS of 22.9 months in the oral azacitidine treated group (43% improvement), and a study duration of 60 months with a drop-out rate of 5% from both treatment arms, over the duration of the study, this design requires 330 deaths and approximately 460 subjects (230 per treatment arm) to be randomized in order to achieve at least 90% power to detect a constant hazard ratio of 0.70 and demonstrate a statistically significant difference in OS. It is assumed that the OS distribution is exponential with a constant failure (hazard) rate and that accrual is non-uniform during an accrual period of 36 months with 25% of the subjects accrued during each of the first 2 years of enrollment (50% accrued at 24 months) and the remaining 50%

accrued during the last year of enrollment. Sample size calculations are based on a one-sided alpha of 0.025 with one interim analysis for futility after 30% of the events have occurred.

Sample size was calculated using the East® Version 5.4 software system [REDACTED] [REDACTED]).

## 5. GENERAL STATISTICAL CONSIDERATIONS

### 5.1. Reporting Conventions

Summary tables, listings, and any supportive SAS output will include a “footer” of explanatory notes that will indicate, at a minimum, the following:

Program source (e.g., SAS program name, including the path that generates the output), source data (e.g. derived dataset, raw datasets, etc) and data extraction date (e.g., the database lock date, run date.)

The purpose of the data extraction date is to link the output to a final database, either active or archived, that is write-protected for replication and future reference. An output date will also appear on each output page and will indicate the date the output was generated by the analysis program. Individual source listings will display all the relative values supporting the corresponding tables and/or figures.

Summary statistics for continuous variables include sample size (n), mean, standard deviation (SDev), median, minimum, the 25th (Q1), and 75th (Q3) percentiles, and maximum. All mean and median values will be formatted to one more decimal place than the measured value. SDev values will be formatted to two more decimal places than the measured value. Minimum and maximum values will be presented to the same number of decimal places as the measured value. Frequency summary for categorical variables includes number and percentage. All percentages will be rounded to one decimal place. Number and percentage values will be presented as xx (xx.x%). All analysis and summary tables will have the population sample size for each treatment arm in the column heading. All p-values (2-sided) will be rounded to 4 decimal places. P-values that round to 0.0000 will be presented as ‘<0.0001’ and p-values that round to 1.000 will be presented as ‘>0.9999’. Confidence intervals (CIs) will be presented as 2-sided 95% CIs unless specified differently in specific analysis. All laboratory data will be reported using standard international (SI) units, unless specified otherwise.

All listings will be sorted for presentation in order of treatment arm, study center, subject, and date of procedure or event.

The day of the first dose of any study drug will be defined as Study Day 1.

Baseline value is defined as the last non-missing value on or before randomization date, unless specified otherwise. If multiple values are present for the same date, the average of these values will be used as the baseline, unless specified otherwise.

### 5.2. Analysis Populations

#### 5.2.1. Intent-to-Treat Population

The Intent-to-Treat (ITT) population includes all subjects who are randomized, regardless of whether they received study treatment or not. Subjects will be analyzed based on randomized treatment arm. The ITT population will be used for the analysis of the primary and secondary efficacy endpoints.

### **5.2.2. Modified Intent-to-Treat Population**

The modified Intent-to-Treat (mITT) population includes all subjects who have met inclusion/exclusion criteria and experienced no protocol violations (as defined below) and have received a minimum of 1 cycle of treatment. Subjects will be analyzed based on randomized treatment arm.

Protocol violations leading to exclusion from the mITT population are defined as any of the following:

- No presence of CR/CRi at baseline as programmatically determined by central laboratory data
- Had at least one inclusion or exclusion criteria violation;

### **5.2.3. Safety Population**

The safety population includes all randomized subjects who have received at least 1 dose of study drug.

Drug exposure and all safety analyses will be based on the safety population, unless specified otherwise.

## 6. SUBJECT DISPOSITION

All subjects screened/randomized will be included in these analyses. The disposition of subjects will be summarized with counts and percentages. Summaries will include the number of subjects screened and randomized.

For subjects randomized, subject disposition will be summarized for analysis population by treatment arm and overall for:

- ITT Population
- mITT Population
- Safety Population

A listing of reasons for exclusion from the mITT Population will be provided. A separate listing will be provided for subjects not randomized (screen failures) with reasons for screening failure. Listings will be provided for subjects randomized but not treated, and for discontinued subjects with reason for treatment discontinuation.

Reasons for discontinuation from the study treatment phase will be collected on the CRF and will be summarized for all randomized subjects with the following

- Disease relapse
- Adverse event
- Subject withdrew consent
- Physician decision (become eligible for allogeneic bone marrow or stem cell transplantation during treatment period)
- Death
- Subject lost to follow-up
- Protocol violation
- Other

Reasons for discontinuation from the study will be collected on the CRF and will be summarized for all randomized subjects with following:

- Death
- Adverse event
- Pregnancy
- Progressive disease
- Lack of efficacy
- Recovery
- Withdrew consent
- Non-compliance with study drug
- Lost to follow-up
- Study terminated by sponsor
- Transition to commercially available treatment
- Protocol violation
- Other

## **7. PROTOCOL DEVIATIONS/VIOLATIONS**

The protocol deviations/violations will be identified and reported by site and assessed by clinical research physician or designee following company standard operational procedure. The protocol violations will be summarized by treatment arm for the ITT population.

A by-subject listing of subjects with protocol deviation in the ITT population will be provided. A by-subject listing of subjects with protocol violations in the ITT population will also be provided.

## 8. DEMOGRAPHICS AND BASELINE CHARACTERISTICS

Summaries for the demographics, baseline characteristics, medical history, prior therapy, and prior medications will be presented for the ITT and safety populations. Data summaries will be presented by treatment and overall. Individual subject listings will be provided to support the tables.

### 8.1. Demographics

Demographic characteristics consist of age, sex, race, ethnicity, geographic region, weight (kg), height (cm), and body mass index (BMI).

Age, height, weight and BMI will be summarized using descriptive statistics. Sex, race, ethnicity, geographic region, and age categories will be summarized with counts and percentages.

Age is calculated as described in section [17.1.2](#).

### 8.2. Baseline Characteristics

Baseline clinical characteristics, including the initial WHO AML classification, type of AML (primary or secondary), cytogenetic risk status at time of induction therapy, MRD status at randomization, prior history of MDS/CMML and type (primary or secondary), Eastern Cooperative Oncology Group (ECOG) Performance Status at randomization, CR/CRi status after induction therapy, CR/CRi status at randomization, consolidation therapy received or not, cycles of consolidation therapy received and reasons of not eligible for transplantation will be summarized using frequency distributions (count and percent).

Baseline clinical characteristics, including percentage of bone marrow blasts (%), peripheral blood blasts (%), Hgb (g/dL), platelet count ( $\times 10^9/L$ ), ANC ( $\times 10^9/L$ ) and WBC ( $\times 10^9/L$ ) will be summarized using descriptive statistics. In general, the baseline value is the last non-missing assessment on or prior to the date of randomization, unless otherwise specified.

The following time intervals will be summarized using descriptive statistics:

- time (months) from initial AML diagnosis to randomization;
- time (months) from start of induction therapy to randomization;
- time (days) from start of induction therapy to first achieving CR/CRi;
- time (days) from first achieving CR/CRi to randomization

Results of the baseline chest x-ray, ECG, pregnancy status will be provided in by-subject listings.

### 8.3. Medical History

A summary of medical history will be presented by system organ class (SOC) and preferred term (PT) according to the Medical Dictionary for Regulatory Affairs (MedDRA) Version 22 using frequency distributions (counts and percentages).

Individual subject listings will be provided to support the table.

## **8.4. Prior Therapy**

### **8.4.1. Prior Induction Therapies and Consolidation Therapies for AML**

All prior induction therapies for AML will be summarized in frequency tabulations (subject counts and percentages). The Anatomical Therapeutic Chemical (ATC) coding scheme of the World Health Organization (WHO) (March 2019 version) will be used to group prior induction therapies for AML into relevant categories for these tabulations.

Similar summary table will be provided for consolidation therapies for AML.

Individual subject listings will be provided to support the summary tables.

### **8.4.2. Prior Cancer History and Related Procedures/Surgeries, Radiation and Regimen Therapies**

By-subject listing of prior cancer history, type of therapy received, diagnostic exams for cancer prior to screening for the study and related prior procedures/surgeries, prior radiation treatment and prior regimen treatments for cancers not under study will be provided.

## **8.5. Prior Medications**

Prior medications are defined as medications that were started on or prior to the date of randomization. Prior medications that continue past the date of randomization will also be reported as concomitant medications. The ATC coding scheme of the WHO (March 2019 version) will be used to group medications into relevant categories for these tabulations.

Individual subject listings will be provided to support the tables.

## 9. STUDY TREATMENTS AND EXTENT OF EXPOSURE

All analyses of treatment exposure will be conducted using the safety population, unless otherwise specified.

Descriptive statistics of treatment duration, cumulative dose, dose intensity and average daily dose will be presented by treatment arm. Individual subject listings of drug exposure as recorded in CRF will be provided to support the tables.

### 9.1. Treatment Duration

Treatment duration and number of days dosed will be summarized by treatment arm.

Treatment duration is defined as treatment end date – first dose date +1, where treatment end date is last dose date + 14 days (the prescribed rest period of each cycle), or the death date, whichever is earlier.

Total Person-years of treatment duration will be calculated as the sum of treatment duration (days)/365.25 across all subjects.

Total number of days dosed is defined as the total number of days the subject took a non-zero dose of study drug.

See Section 17.1.3 for cycle length and cycle number calculations. Average cycle length (days), average number of days dosed per cycle, and number of treatment cycles will be summarized by treatment arm. The number of days dosed per cycle is defined as the number of days the subject received a non-zero dose within that cycle. Average cycle length for a subject is defined as treatment duration in days divided by the number of cycles. Number of days dosed per cycle is defined as the total number of days dosed during the entire treatment period /number of cycles. For average cycle length and average number of days dosed per cycle, a single average value will be computed for each subject and then the descriptive statistics will be computed for each treatment arm. Additionally, the count and percent of subjects by number of cycles of treatment will be provided for each treatment arm.

### 9.2. Cumulative Dose and Dose Intensity

Cumulative dose is defined as the sum of all doses taken across the entire treatment period (in mg). Average daily dose (mg/day) is defined as the cumulative dose divided by the total number of days dosed.

Actual dose intensity during the treatment is defined as the cumulative dose divided by the treatment duration, which is defined as in Section 9.1.

Relative dose intensity (RDI) is defined as the ratio of actual dose intensity to the planned dose intensity, which is  $300\text{mg/day} \times 14 \text{ days}/28\text{days}=150\text{mg/day}$  for all subjects.

The overall relative dose intensity will be categorized into < 75%, 75% to 85%, 85% to 100%, and > 100%, and frequency counts will be provided by treatment arm.

In addition, treatment exposure as described in section 9.1 and 9.2 will also be analyzed for subjects with dose escalation, which is defined as subjects who have at least one assigned dose

regimen of 300mg × 21/28 days. In these analyses, the first dose date refers to the first dose date of the treatment period where the assigned dose regimen is 300mg × 21/28 days.

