8.2.5. Dose Modifications for Toxicity

Subjects should be monitored for toxicity using the National Cancer Institute Common Terminology Criteria for Adverse Events (NCI-CTCAE), Version 4.0, as a guide for the grading of severity.

If a certain level of toxicity is observed and considered by the investigator to be at least possibly related to treatment, IP dosing may be interrupted, delayed or modified. The Investigator is encouraged to contact the Medical Monitor prior to any treatment adjustment.

A maximum of one dose reduction to a daily dose of 200 mg is permitted in the event of toxicity. If toxicity persists, a maximum of one treatment schedule modification from 14 to 7 days (21 days to 14 days for those subjects whose dose schedule has been extended due to disease progression) is permitted in the event of continuing toxicity that does not respond to dose reduction. The decision to modify a subject's treatment schedule from 14 to 7 days (21 days to 14 days for those subjects whose dose schedule has been extended due to disease progression) should first be discussed with the Medical Monitor or designee. Subjects should not receive less than 200 mg IP or be scheduled to receive treatment for less than 7 days.

Subjects who have their IP dose reduced or treatment schedule modified may return to their original dose and/or schedule in a step-wise fashion upon discussion and agreement between the investigator and the Medical Monitor provided that the increased dose or treatment schedule is

tolerable and at least two additional treatment cycles have occurred since the dose reduction or treatment schedule modification. The treatment schedule should first be increased from 7 to 14 days, followed by a dose escalation step from 200 to 300 mg.

Dose Modification for Febrile Neutropenia \geq Grade 3

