### 9.4. Treatment Compliance

As part of the routine recording of the amount of IP taken by each subject, the dose start and end dates, dose assigned and actual dose administered will be recorded in the CRF. These records will be used to calculate compliance.

The compliance rate (%) for each subject will be computed as 100 times the cumulative dose (in mg) taken over the period divided by the intended cumulative dose (in mg) that should have been taken over the same period. It will be calculated for each subject for each cycle of treatment and overall.

Overall compliance will be summarized using descriptive statistics overall and by cycle. Additionally, the number and percentage of subjects will be summarized by category < 75%, ≥75 to ≤ 120%, and > 120%.

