- serious TEAEs by decreasing order of frequency of PT;
- serious TEAEs related to study medication;
- serious TEAEs with severity of grade 3 or 4;
- serious TEAEs related to study medication with severity of grade 3 or 4;
- TEAEs leading to study medication discontinuation;
- TEAEs leading to dose reduction of study medication;
- TEAEs leading to dose interruption of study medication;
- TEAEs leading to dose interruption and reduction of study medication;
- TEAEs by sex;
- TEAEs by age group (< 65, ≥ 65 to 75, and ≥ 75years);
- TEAEs by race group (White, Asian, Black or Others);
- TEAEs by ECOG performance status (0 or 1, 2 or 3)

Additionally, the incidence rate per 100 person-years will be summarized for all TEAEs and Grade 3 or 4 TEAEs by system organ class, preferred term, and treatment arm. The incidence rate per 100 person-years is calculated as  $(100*n)/T$ , where n is the number of subjects with the given AE at the system organ class or preferred term level, and T is total person-years of exposure. If a subject has multiple events with the same preferred term, then the time to the first event is used. For subject with no event, time to earlier of last dose + 28 days or death date is used.

Subjects with multiple events reported for the same preferred term will be counted only once per system organ class and preferred term level. For summaries by severity (CTCAE grade), subjects with multiple events at the preferred term level will be counted once and for the highest reported severity. For summaries by treatment cycle, subjects with multiple events reported with

a start date within the same cycle for the same preferred term will be counted once per system organ class level and preferred term level within the cycle.

In summaries of TEAEs related to study medication, if a subject reports multiple occurrences of the same AE, only the related occurrence will be summarized. Adverse events with missing relationship to study medication will be imputed as related to study medication.

Additional safety analysis may be performed, displayed and summarized, when deemed necessary.

To assess the safety profile among subjects who have dose escalation, defined as subjects who have at least one assigned dose of 300mg × 21/28 days, the following summary tables will be provided in subjects with dose escalation:

- First occurrence of TEAE by dose schedule period (300mg × 14/28days, 300mg × 21/28days);

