### 17.1.3. Calculation of Cycles

The start date of each treatment cycle will be calculated based on study drug exposure records for each subject. The start date of the first cycle will be the earliest date the subject receives any study drug.

Once the start dates, e.g.,  $S_1, S_2, S_3 \dots$  are calculated, the end date of each cycle is calculated as the day before the start date of the following cycle, i.e.,  $E_i = S_{i+1} - 1$ . For the last cycle, the end date will be the same as the treatment end date, which is calculated as the last dose date +14 days (the prescribed rest period of each cycle), or the death date, whichever is earlier.

The cycle number for each data of interest, e.g., AE or lab, will be calculated based on the cycle window set by their start and end dates. If a date is on or after  $S_i$  and before  $S_{i+1}$ , the corresponding cycle number will be  $i$ .

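### The SAP keeps a 14-day rest period for subjects ending treatment on 300 mg x 21/28, which adds up to 7 days to treatment duration and understates dose intensity

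*SAP*

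**What the plan says.** SAP 9.1 computes treatment duration from the first dose to a treatment end date. Unless death comes first, "treatment end date is last dose date + 14 days (the prescribed rest period of each cycle"). SAP 17.1.3 closes the last cycle on the same date, "which is calculated as the last dose date +14 days (the prescribed rest period of each cycle"). Neither section has a variant for another schedule.

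In SAP 9.2, "Cumulative dose is defined as the sum of all doses taken across the entire treatment period (in mg"), and actual dose intensity is that sum divided by the duration from 9.1. Then "Relative dose intensity (RDI) is defined as the ratio of actual dose intensity to the planned dose intensity", and the planned value is fixed at 150 mg/day for everyone.

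SAP 9.2 also applies all of this to subjects with at least one assigned regimen of 300 mg x 21/28. For that analysis it redefines only the start: "the first dose date refers to the first dose date of the treatment period where the assigned dose regimen is 300mg × 21/28 days". The end date is not mentioned.

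Protocol 8.2.6 provides for the 21-day schedule, and Protocol section 6 sets a cycle at 28 days.

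**The concern.** The SAP justifies its 14-day constant as the rest period of each cycle. That is true of the 14-day schedule and not of the 21-day schedule, which leaves 28 - 21 = 7 days. The escalated-period analysis isolates exactly the regimen for which the justification fails.

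The surplus is added once, at the end of treatment, so it weighs most on subjects with few escalated cycles. Dose intensity in that table then depends on how many 21-day cycles were received as well as on how well they were taken. A reader could take a value below the schedule's nominal 225 mg/day for missed doses when none were missed. The same end date enters whole-treatment duration, person-years, dose intensity and average cycle length for any subject whose last dose was under 21/28. What is at stake is the accuracy of descriptive exposure tables.

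**Working it through.** **Inputs.** Cycle length 28 days (Protocol section 6); 300 mg daily; 14 dosing days on the starting schedule and 21 on the escalated one (Protocol 8.2.1 and 8.2.6); end of treatment at last dose + 14 days (SAP 9.1, 17.1.3); planned intensity 150 mg/day (SAP 9.2). The figure of 225 mg/day is derived here as 300 x 21/28; the SAP does not state it.

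**Assumptions.** k undelayed cycles, every dose taken, last dose on the final dosing day, survival of at least 14 days after it, and doses counted only from the start of the period analysed.

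**Formula.** With D dosing days per cycle and R rest days, duration = 28(k - 1) + D + R and intensity = 300 x D x k / duration.

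**The plan's own figure.** With D = 14 and R = 14, k = 1 gives 4200/28 = 150 mg/day and k = 6 gives 25200/168 = 150. On the starting schedule the rule returns the planned intensity whatever the number of cycles.

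**The 21/28 period as written.** With D = 21 and R = 14, duration = 28k + 7 and intensity = 6300k/(28k + 7). With R = 7, duration = 28k and intensity = 6300k/28k = 225 for every k.

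| Cycles k | Dose (mg) | Days as written | Days with R = 7 | Intensity as written (mg/day) | Intensity with R = 7 | RDI as written | RDI with R = 7 |
|---|---|---|---|---|---|---|---|
| 1 | 6300 | 35 | 28 | 180.0 | 225 | 120% | 150% |
| 2 | 12600 | 63 | 56 | 200.0 | 225 | 133% | 150% |
| 3 | 18900 | 91 | 84 | 207.7 | 225 | 138% | 150% |
| 6 | 37800 | 175 | 168 | 216.0 | 225 | 144% | 150% |

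RDI is intensity divided by 150. The shortfall from 225 is 20% at k = 1 and 4% at k = 6. Average cycle length at k = 1 is 35 days instead of 28. The surplus is 7/365.25 = 0.019 person-years per subject.

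**Whole treatment.** For p full 14-day cycles followed by k full 21-day cycles, duration is 28(p + k) + 7 instead of 28(p + k). As an illustration with p = 3 and k = 1 (assumed): (12600 + 6300)/119 = 158.8 mg/day, against 18900/112 = 168.8. The same 7 days are present and their weight is smaller.

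**Where the figures do not hold.**
- Last dose on day 14 of the only 21/28 cycle: 14 + 14 = 28 days, so no day falls beyond the cycle, and 4200/28 = 150 mg/day.
- Death 7 days after the last dose: the cap at death gives 6300/28 = 225 at k = 1. Earlier death gives more than 225.
- A 14-day delay between two cycles: 12600/77 = 163.6 mg/day as written (RDI 109%) and 12600/70 = 180 with R = 7. The surplus is still 7 days, but neither value is 225.
- A subject moved back in the way Protocol 8.2.5 allows ("21 days to 14 days for those subjects whose dose schedule has been extended due to disease progression") who ends on the 14-day schedule: the 14-day constant fits.

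**The case against.** The best defence is that little turns on this. All RDI values in the table exceed 100% before and after correction, so these subjects stay in the SAP's top RDI category. No test of exposure between arms is planned. Adherence has its own measure in SAP 9.4, which compares dose taken with dose intended and uses no rest period. All of that stands, and it is why the point is minor. It does not rescue the rule: the continuous summaries of duration, intensity and cycle length still carry a rest period that the schedule does not have.

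Several stronger readings are tempting, and the documents do not support them.

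- A reader might infer that every escalated subject gains 7 days. The full surplus needs a last dose on day 21 and survival of 14 days.
- A reader might infer that pre-escalation doses enter the numerator over a post-escalation denominator, giving extreme RDI values. SAP 9.2 nowhere directs this. Once the clock is reset, the treatment period in the cumulative-dose definition naturally means the escalated period. One confirming sentence is enough.
- A reader might call 150 mg/day the wrong denominator. The SAP declares it for all subjects, so it is a reference to the starting regimen and not an error.
- A reader might infer a distorted comparison between arms. The documents give no number of escalated cycles by arm, so no such contrast can be shown.
- Protocol 8.2.6 also lists 200 mg for 21 days as an escalation step, which the SAP category does not count. That is a separate labelling matter; SAP 9.3 names its category explicitly.

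**Conclusion.** The point holds as an error of definition in SAP 9.1 and 17.1.3 that SAP 9.2 carries into the 300 mg x 21/28 analysis. For a subject who ends on day 21 of a 21/28 cycle and lives at least 14 days more, treatment duration is 7 days too long in both the escalated-period and the whole-treatment summaries. Under undelayed cycles, full dosing and doses counted from the reset date, escalated-period intensity is understated by between 20% (one cycle) and 4% (six cycles).

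The numerical effect is confined to descriptive exposure summaries. OS, RFS, alpha, power and SAP 9.4 compliance do not use the constant. The general adverse event rates in SAP 12.1 have their own rule: "For subject with no event, time to earlier of last dose + 28 days or death date is used". SAP 12.1 also plans exposure-adjusted rates by dose-schedule period but states no person-time rule for those periods, so nothing can be said about whether they are affected.

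**What to change.** In SAP 9.1 and 17.1.3, and so in both SAP 9.2 analyses, set the treatment end to last dose + (28 minus the dosing days of the schedule assigned at the last dose), or death if earlier. That gives 7 days on 21/28 and leaves 14 days on 14/28. In SAP 9.2, confirm that cumulative dose in the escalated analysis counts doses from the reset first dose date. Keep 150 mg/day as the declared reference and label it 'relative to starting regimen'. Replacing it with 225 while keeping the 14-day constant would show full adherence as 180/225 = 80% at one cycle and 216/225 = 96% at six.

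The cost is a few sentences and a small program change. The data should be to hand, since SAP 9.4 says that "the dose start and end dates, dose assigned and actual dose administered will be recorded in the CRF".

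Three consequences should be accepted knowingly.

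- A subject who stops dosing early in the last cycle still gets a shortened final cycle, as now happens on the 14-day schedule. With a last dose on day 14 of the only 21/28 cycle, the new rule gives 4200/21 = 200 mg/day (RDI 133%), against 150 mg/day (RDI 100%) at present, so that subject's RDI category would change.
- For subjects ending on the 7-day schedule of Protocol 8.2.5, the same rule gives 21 rest days. One full cycle of 200 mg x 7 then shows 1400/28 = 50 mg/day instead of 1400/21 = 66.7.
- SAP 17.1.3 also uses cycle windows to place adverse events and laboratory values, so tables by cycle should be checked when the last-cycle end date moves.
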